8.3 Dose modifications for lenalidomide based on adverse events during a cycle

→ → Use the NCI Common Terminology Criteria for Adverse Events (CTCAE) version 4.0* unless otherwise specified ← ←

CTCAE System/Organ/Class (SOC)	ADVERSE EVENT	AGENT	ACTION** Days 2-14 of cycle	ACTION** Day ≥15 of cycle
Blood and lymphatic system disorders	Febrile neutropenia associated with fever (temperature ≥38.5°C)	Lenalidomide	Omit lenalidomide dose. Follow CBC weekly. If neutropenia has resolved to ≤Grade 2 prior to Day 35, restart lenalidomide at next lower dose level and continue the cycle through Day 35. If neutropenia is the only toxicity for which a dose reduction is required, G-CSF may be used and the lenalidomide dose maintained	Omit lenalidomide for remainder of cycle. See Section 8.11 for Initiation of a New Cycle and reduce the dose of lenalidomide by 1 dose level. If neutropenia is the only toxicity for which a dose reduction is required, G-CSF may be used and the lenalidomide dose maintained for the next cycle at the investigator's discretion.
Investigations	Platelet count decreased ≥Grade 3 (platelet count <50,000/mm ³)	Lenalidomide	Omit lenalidomide dose Follow CBC weekly Hold anticoagulation until platelets >50,000 If thrombocytopenia resolves to ≤Grade 2 prior to Day 35, restart lenalidomide at next lower dose level and continue the cycle through Day 35	Omit lenalidomide for remainder of cycle See Section 8.11 , Instructions for Initiation of a New Cycle and reduce the dose of lenalidomide by 1 dose level
Skin and subcutaneous tissue disorders	Rash maculo papular Grade 2 or 3.	Lenalidomide	Omit lenalidomide dose Follow weekly If the event resolves to ≤Grade 1 prior to Day 35, restart lenalidomide at next lower dose level and continue the cycle through Day 35	Omit lenalidomide for remainder of cycle See Section 8.11 , Instructions for Initiation of a New Cycle and reduce the dose of lenalidomide by 1 dose level
	Any rash Grade 4	Lenalidomide	Discontinue lenalidomide	Discontinue lenalidomide

CTCAE System/Organ/Class (SOC)	ADVERSE EVENT	AGENT	ACTION** Days 2-14 of cycle	ACTION** Day \geq15 of cycle
Nervous System Disorders	Peripheral sensory neuropathy Grade 3	Lenalidomide	Omit lenalidomide dose Follow at least weekly If the event resolves to \leq Grade 1 prior to Day 35, restart lenalidomide at next lower dose level and continue the cycle through Day 35	Omit lenalidomide for the remainder of the cycle. See Section 8.11 Instructions for Initiation of a New Cycle and reduce the dose of lenalidomide by 1 dose level
	Peripheral sensory neuropathy Grade 4	Lenalidomide	Discontinue lenalidomide	Discontinue lenalidomide
Immune system disorders	Allergic reaction Grade 2-3	Lenalidomide	Omit dose Follow at least weekly If the toxicity resolves to \leq Grade 1 prior to Day 35 restart at next lower dose level and continue the cycle until Day 35	Omit lenalidomide for the remainder of the cycle If the adverse event resolves to \leq Grade 1, reduce dose 1 level in next cycle If adverse event recurs, discontinue therapy
	Grade 4	Lenalidomide	Discontinue lenalidomide	Discontinue lenalidomide
Vascular disorders	Thromboembolic event \geq Grade 3	Lenalidomide	Omit dose and start anticoagulation; restart at investigator's discretion (maintain dose level)	Omit lenalidomide for remainder of cycle and start anticoagulation. Maintain dose level in next cycle
Kidney and Urinary System	Renal Insufficiency	Lenalidomide	CrCl $>$ 50 mL/min: No adjustment CrCl 30-50 mL/min: 10 mg/day CrCl $<$ 30 mL/min (no dialysis): 15 mg every 48 hours CrCl $<$ 30 mL/min (dialysis): 5 mg daily (after HD (hemodialysis) on HD days)	

CTCAE System/Organ/Class (SOC)	ADVERSE EVENT	AGENT	ACTION** Days 2-14 of cycle	ACTION** Day \geq 15 of cycle
Endocrine disorders	Hyperthyroidism or Hypothyroidism \geq Grade 2	Lenalidomide	Omit lenalidomide for remainder of cycle, evaluate etiology, and initiate appropriate therapy. See Instructions for Initiation of a New Cycle and reduce the dose of lenalidomide by 1 dose level	Omit lenalidomide for remainder of cycle, evaluate etiology, and initiate appropriate therapy. See Section 8.11 , Instructions for Initiation of a New Cycle and reduce the dose of lenalidomide by 1 dose level
Other non-hematologic adverse event	Other non-hematologic toxicity \geq Grade 3	Lenalidomide	Omit lenalidomide dose Follow at least weekly If AE resolves to \leq Grade 2 prior to Day 35, restart lenalidomide at next lower dose level and continue the cycle through Day 35	Omit lenalidomide for remainder of cycle See Section 8.11 , Instructions for Initiation of a New Cycle and reduce the dose of lenalidomide by 1 dose level.

* Located at http://ctep.cancer.gov/protocolDevelopment/electronic_applications.ctc.htm

** Use the following to describe actions in the Action column:

- Omit = The current dose(s) for the specified drug(s) during a cycle is skipped. The patient does not make up the omitted dose(s) at a later time
- Hold/Delay = The current dose(s) of all drugs during a cycle is delayed. The patient does make up the delayed dose(s) when the patient meets the protocol criteria to restart drugs
- Discontinue = The specified drug(s) are totally stopped

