8.11 Instruction for initiation of a new cycle of therapy

A new cycle of treatment may begin on the scheduled Day 1 of a new cycle if:

- The ANC is $\geq 1000/\mu\text{L}$
- The platelet count is $\geq 50,000/\mu\text{L}$
- Any other non-hematologic drug-related adverse event that may have occurred has resolved to \leq Grade 1 or baseline severity.

If these conditions are not met on Day 1 of a new cycle, dosing should be delayed for 1 week. At the end of that time, the patient should be re-evaluated to determine whether the criteria have been met. If the patient continues to fail to meet the above-cited criteria, delay therapy and continue to re-evaluate.

If any drug dosing was halted during the previous cycle and was restarted with a one-level dose reduction without requiring an interruption for the remainder of the cycle, then that reduced dose level will be initiated on Day 1 of the new cycle.

If any drug dosing was omitted for the remainder of the previous cycle or if the new cycle is held due to known hematologic toxicity newly encountered on the scheduled Day 1, then the new cycle will be started with a one-level dose reduction. If a new cycle of therapy cannot be restarted within 4 weeks of the scheduled Day 1 due to non-resolution of drug related toxicities, the patient will be removed from protocol therapy and will go to event monitoring.

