Drug will be shipped directly to the patient through Revlimid REMS Program. Any unused lenalidomide should be returned for disposition in accordance with the REVLIMID REMS™ program.

15.29 **Nursing Guidelines**

15.291 The most common side effects are neutropenia and thrombocytopenia.

15.292 Due to the highly teratogenic potential of the closely related thalidomide, it is highly recommended that all women of childbearing age group and all men use effective contraception during therapy. All staff who are pregnant or who can become pregnant should not handle this drug outside of its original packaging.

15.293 Instruct patient to report any rash immediately to the study team.

15.294 Lenalidomide capsules should be swallowed whole, and should not be broken, chewed or opened.

15.295 If a dose of lenalidomide is missed, it should be taken as soon as possible on the same day. If it is missed for the entire day, it should not be made up.

15.296 Patients who take more than the prescribed dose of lenalidomide should be instructed to seek emergency medical care if needed and contact study staff immediately.

15.3 **Dexamethasone for Oral Administration (DXM)**

15.31 **Background:** Dexamethasone is an adrenal corticosteroid compound. Dexamethasone decreases inflammation by suppression of neutrophil migration, decreased production of inflammatory mediators, and reversal of increased capillary permeability; suppresses normal immune response. Dexamethasone's mechanism of antiemetic activity is unknown.

15.32 **Formulation:** Commercially available for oral administration as:
Tablets [scored]: 0.5 mg, 0.75 mg, 1 mg, 1.5 mg, 2 mg, 4 mg, and 6 mg.

Solution, oral: 0.5 mg/mL (500 mL).

Solution, oral concentrate: Dexamethasone Intensol: 1 mg/mL (30 mL).

- 15.33 **Preparation, storage, and stability:** Refer to package insert for complete preparation and dispensing instructions. Store oral tablets at room temperature between 20°C to 25°C (60°F to 77°F). Protect from moisture. Dispense in a well-closed, light-resistant container as defined in the USP/NF. Store oral liquid at room temperature, do not freeze. Do not use if solution contains a precipitate. Refer to commercial package for drug expiration date.
- 15.34 **Administration:** Refer to the treatment section for specific administration instructions. May be taken with meals to decrease GI upset.
- 15.35 **Pharmacokinetic information:**
Onset of action: Prompt
Duration of metabolic effect: 72 hours

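### Section 8.3 gives no lenalidomide action for mid-cycle neutropenia without fever, although 8.11 acts on a milder Day 1 count and 8.2, read literally, acts on pembrolizumab

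*Combined protocol and SAP*

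**What the plan says.** Section 8.3 sets lenalidomide changes for events within a cycle, with one column for Days 2-14 and one for Day 15 onward.

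- Its only neutropenia row is "Febrile neutropenia associated with fever (temperature ≥38.5°C"). In the earlier column lenalidomide is omitted, counts are followed weekly, and the drug restarts one level lower "If neutropenia has resolved to ≤Grade 2 prior to Day 35". In the later column it is omitted for the rest of the cycle and then reduced by one level. Both columns allow G-CSF with the dose maintained when neutropenia is the only toxicity calling for a reduction.
- The other blood-count row is "Platelet count decreased ≥Grade 3", defined by a count below 50,000/mm³ with no symptom required.
- The last row, "Other non-hematologic adverse event", begins at Grade 3.

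Section 8.11 requires an ANC of at least 1000/µL on Day 1 of a new cycle. If the start criteria are not met, dosing waits one week and the patient is re-evaluated. There are two routes to starting one level lower. One is that a drug was left out through the end of the prior cycle. The other applies "if the new cycle is held due to known hematologic toxicity newly encountered on the scheduled Day 1".

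The final row of Section 8.2 covers all other drug-related adverse events and is not limited to non-hematologic ones. Pembrolizumab is omitted at Grade 3 or severe and permanently discontinued at Grade 4. Section 8.4, for dexamethasone, has no neutropenia row.

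Section 8.0 makes the modifications strict for the first two cycles and guidelines after that. The schedule in Section 4.1 has weekly blood counts in those same two cycles. Of lenalidomide, Section 15.291 says: "The most common side effects are neutropenia and thrombocytopenia".

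**The concern.** The protocol names two leading lenalidomide toxicities. For one, thrombocytopenia, the mid-cycle table acts on the count. For the other, neutropenia, it acts only if the patient also has a fever. The Day 1 rule then acts on the neutrophil count without fever. Taken together, the lenalidomide rules can respond to a shallower fall and not to a deeper one, depending on the day the count is drawn.

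What is at stake is patient safety and a table that can be followed as written. In the first two cycles the treating physician is told to follow it strictly and has a weekly neutrophil count in hand. For a low count without fever, the lenalidomide table says nothing. The pembrolizumab table may at the same time call for that drug to be omitted or stopped.

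**Working it through.** The plan states no figure on this point and no arithmetic decides it. The check is to look in every row of 8.2, 8.3 and 8.4, and in 8.0, 8.11, 9.5, 10.8 and the test schedule, for a rule that applies to neutropenia without fever during a cycle.

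**Step 1: can the febrile row be read to include afebrile cases?** Its recovery and G-CSF wording speaks of neutropenia alone, which might suggest a wider reading. But its trigger names fever and a temperature, and Section 10.8 lists a decreased neutrophil count and febrile neutropenia as two separate terms to be graded. On the text, the row is febrile only.

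**Step 2: does any other row of 8.3 apply?** The catch-all is confined to non-hematologic events, and no other row mentions neutrophils. So 8.3 has no lenalidomide instruction for afebrile neutropenia at any depth, in either day column.

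**Step 3: follow illustrative patients through the rules.** The counts are examples, not data.

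| Situation | 8.3 (lenalidomide, mid-cycle) | 8.11 (next Day 1) | 8.2 catch-all (pembrolizumab) |
|---|---|---|---|
| ANC 900 first seen on Day 1, no fever | Not applicable | 900 < 1000: one-week delay, then one level lower | Depends on grade and attribution |
| ANC 300 on Day 8, no fever, 1000 by next Day 1 | No row applies | 1000 ≥ 1000: ANC criterion met; nothing was omitted under 8.3, so neither route to a reduction opens | If drug-related: omit at Grade 3, permanently discontinue at Grade 4 |
| ANC 300 on Day 8 with temperature ≥38.5°C | Omit; restart one level lower on recovery, or G-CSF with dose maintained | As applicable | As above |
| Platelets below 50,000 on Day 8, no symptoms | Omit; restart one level lower on recovery | As applicable | As above |

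Rows one and two show the inversion: the lower count leaves lenalidomide unchanged, and the higher count delays and reduces it. Rows two and four show the asymmetry between the two blood-count toxicities.

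**Step 4: compare the drugs.** In row two, a Grade 4 event judged drug-related would permanently stop pembrolizumab under 8.2 while 8.3 does not address lenalidomide.

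**Step 5: check how binding this is.** Section 8.0 makes the tables strict in cycles 1 and 2, and the weekly counts fall in the same cycles. Section 9.5 allows growth factors as clinically warranted, which is supportive care and not a lenalidomide dose rule.

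**The case against.** The strongest reply is that the two sections do different jobs. Section 8.11 decides whether a new cycle may start and 8.3 governs events within one, so both can be obeyed. Confining mid-cycle action to febrile cases may also be deliberate, since the protocol elsewhere treats isolated low counts as expected. Section 10.6 exempts a decreased neutrophil count up to Grade 4 from expedited reporting when there is no hospitalization, and the stopping rule in Section 16.42 counts non-hematologic events only. From cycle 3 the tables are only guidelines.

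Much of this stands. The fault is a gap and a mismatch in ordering, not two instructions that cannot both be followed, and the choice may be intended. But the protocol does not say so, and the count-only platelet row and the fever-free Day 1 rule both weigh against that reading. Later discretion does not cover the two strict cycles.

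A reader might infer that such a fall triggers no action of any kind. The documents do not support that, because the 8.2 catch-all can act on pembrolizumab. Nor are the weekly counts without use: they also serve the platelet row and follow-up within the febrile row.

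A reader might also infer that practice will diverge between sites. Sections 6.16 and 7.3 require treatment to begin at Mayo Clinic, with returns there each cycle and no treatment by a local doctor, so that inference is weak.

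**Conclusion.** The point holds for lenalidomide. Section 8.3 is silent on mid-cycle neutropenia without fever, and taken with 8.11 it can order the lenalidomide response inversely to severity. Section 8.2, read literally, acts on pembrolizumab for an event that 8.3 leaves open. The passages need to be reconciled on grounds of patient safety and internal consistency.

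This rests on three readings:

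- The febrile row means what its trigger says.
- The one-level reduction in 8.11, which names no drug, reaches lenalidomide. Section 8.0 ties reductions to attribution, and 15.291 lists neutropenia among this drug's most common effects.
- Drug-related in the 8.2 catch-all is not limited to events attributed to pembrolizumab alone. If it is so limited, the 8.2 part applies to fewer events and the mismatch between 8.3 and 8.11 is unchanged.

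The size cannot be put in patients. A reader might apply the 37% from the Background to the 37 evaluable patients (0.37 × 37 = 13.7). That figure is Grade 3 or higher myelosuppression, not neutropenia, in heavily pretreated patients over a median of 7 cycles. It also does not isolate afebrile falls that recover by Day 1. A reader might also infer a distortion of the primary response rate. The documents show no such effect, and in a single-arm study no difference in exposure between arms can arise.

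**What to change.** The sponsor should reconcile Sections 8.2, 8.3 and 8.11 for Grade 3-4 neutropenia without fever. The text should make clear, for both day columns of 8.3, whether such an event falls under the existing neutropenia row, under a rule of its own, or needs no lenalidomide action during the cycle. It should also say whether the 8.2 catch-all is meant to apply to it. The mid-cycle and Day 1 rules should then be consistent with severity, or the protocol should state that the difference is intended. The content of the rule is for the clinical team.

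The cost is one table row or one or two sentences, in an amendment that goes to the IRB under Section 6.2. No sample size, endpoint or analysis changes.

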4.0 Test Schedule

4.1 Schedule of assessments

Tests and Procedures	Screening		Active Treatment ¹						
	≤30 days	≤14 days	Cycles 1-3 to be repeated beyond 3 cycles						
			Cycle 1		Cycle 2		Cycle 3		End of Induction treatment
			Weekly (For first 2 cycles)	Cycle 1, Day 1, Pre-treatment ¹⁰	Pembrolizumab infusion Cycle 1, Day 22, Pre-treatment ¹¹	Cycle 2, Day 1, Pre-treatment	Pembrolizumab infusion Cycle 2, Day 15, Pre-treatment ¹¹	Cycle 3, Day 1, Pre-treatment	
Complete medical history	X								
Adverse Event monitoring		X		X		X		X	X
Physical exam, including weight, vital signs		X		X		X		X	X
Height		X							
Performance status (ECOG scale)		X		X		X		X	X
CBC with diff (includes hemoglobin, ANC, WBC with complete differential, platelets)		X	X	X	X	X	X	X	X
Prothrombin time (PT)	X								
Chemistry group to include sodium, potassium, glucose, alkaline phosphatase; Total and Direct bilirubin; SGOT (AST); SGPT (ALT); serum creatinine, calcium		X	X	X	X	X	X	X	X
LDH, Beta ₂ -microglobulin, Plasma cell assessment	X								
sTSH	X			Every 6 months while on treatment					
Electrophoresis of serum and urine (SPEP/UPEP)		X		X ⁹		X ⁹		X ⁹	X ⁹
Affected Immunoglobulin ²		X		X		X		X	X
Immunofixation serum and urine	X			X ³		X ³		X ³	X ³
Immunoglobulin free light chain		X		X ⁴		X ⁴		X ⁴	X ⁴
X-ray skeletal survey or low dose whole body CT	X								
Bone marrow aspirate and biopsy, myeloma FISH, plasma cell proliferation, and flow cytometry	X			X ⁵		X ⁵		X ⁵	X ⁵

	Screening		Active Treatment ¹							
	≤30 days	≤14 days	Cycles 1-3 to be repeated beyond 3 cycles							
			Cycle 1		Cycle 2		Cycle 3		End of Induction treatment	
			Weekly (For first 2 cycles)	Cycle 1, Day 1, Pre-treatment ¹⁰	Pembrolizumab infusion Cycle 1, Day 22, Pre-treatment ¹¹	Cycle 2, Day 1, Pre-treatment	Pembrolizumab infusion Cycle 2, Day 15, Pre-treatment ¹¹	Cycle 3, Day 1, Pre-treatment		Pembrolizumab infusion Cycle 3, Day 8, Pre-treatment ¹¹
Tests and Procedures										
Research bone marrow ^R (IRB 521-93)	X			X ⁵		X ⁵		X ⁵		X ⁵
Research blood sample ^R (IRB 521-93)	X			X ⁶		X ⁶		X ⁶		
Chest x-ray	X									
Serum pregnancy test		X ⁷								
Patient Medication Diary (Appendix II) ⁸ .				X		X		X		X

Cycle length during induction = 28 days

- 1) All scheduled visits will have a window of ± 4 days, except pembrolizumab infusion days which will have a window of ± 1 day

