7.0 Protocol Treatment

7.1 Treatment Schedule

Cycle length: 28 days.

Agent	Route	Dose	Day	Retreatment
Lenalidomide	PO	25 mg*	1-21	Every 28 days
Pembrolizumab	IV	200mg	Every 21 days	Every 21 days
Dexamethasone	PO	40 mg	1, 8, 15, 22	Every 28 days

* If the patient has renal insufficiency, lenalidomide dose modifications should be made according to the following criteria:

CrCl >50 mL/min: No adjustment

CrCl 30-50 mL/min: 10 mg/day

CrCl <30 mL/min (no dialysis): 15 mg every 48 hours

CrCl <30 mL/min (dialysis): 5 mg daily (after HD (hemodialysis) on HD days)

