7.3 Patient return to Mayo Clinic

For this protocol, the patient must return to the consenting institution (Mayo Clinic) for evaluation every 21 days on the days of infusion while receiving pembrolizumab. (If pembrolizumab has been discontinued these visits are not required.) In addition, the patient must return every 28 days on Day 1 of each cycle while receiving any study treatment. Treatment by a local medical doctor (LMD) is not allowed.

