8.0 Dosage Modification Based on Adverse Events

Strictly follow the modifications in this table for the first **two** cycles, until individual treatment tolerance can be ascertained. Individual drugs can be dose reduced as per the table below depending on the adverse event attribution. Thereafter, these modifications should be regarded as guidelines to produce mild-to-moderate, but not debilitating, side effects. If multiple adverse events are seen, administer dose based on greatest reduction required for any single adverse event observed. Reductions apply to treatment given in the preceding cycle and are based on adverse events observed since the prior dose.

ALERT: ADR reporting may be required for some adverse events (See Section 10)

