8.1 Dose Levels for each drug in the combination

	Pembrolizumab (Every 21 days)	Lenalidomide (Days 1-21)	Dexamethasone (Days 1, 8, 15, 22)
Starting dose	200 mg	25 mg	40 mg
-1		15 mg	20 mg
-2		10 mg	12 mg
-3		5 mg	4 mg
-4		Discontinue	Discontinue

Note: If pembrolizumab is discontinued, the patient may continue treatment with the remaining drugs. If lenalidomide is discontinued, patient will go to event monitoring.

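### Six lenalidomide rows in Section 8.3 run the cycle to Day 35, which conflicts with the 28-day cycle and Days 1-21 dosing and leaves the dosing days and next Day 1 unstated

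*Combined protocol and SAP*

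**What the plan says.** The cycle is fixed in several places. Section 7.1 gives "Cycle length: 28 days", and the Section 4.1 schedule and the schema footnote agree. Sections 7.1 and 8.1 put lenalidomide on Days 1-21. Section 7.1 puts dexamethasone on Days 1, 8, 15 and 22. Section 7.3 says "the patient must return every 28 days on Day 1 of each cycle while receiving any study treatment". The patient diary in Appendix II ends at Day 28.

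The Days 2-14 column of Section 8.3 says something else in six rows: febrile neutropenia, platelet count decreased, maculopapular rash Grade 2 or 3, peripheral sensory neuropathy Grade 3, allergic reaction Grade 2-3, and other non-hematologic toxicity of Grade 3 or higher. Each starts with the action Omit, allows restart if the event resolves before Day 35, and then directs the site to "restart lenalidomide at next lower dose level and continue the cycle through Day 35". The allergic reaction row runs the cycle until Day 35, with the same meaning. The footnote to the table defines Omit as skipping doses that are not made up later.

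Two other rules bear on this. Section 8.0 says "Strictly follow the modifications in this table for the first" two cycles; after that the tables are guidelines. Section 8.11 covers the start of a new cycle: "If these conditions are not met on Day 1 of a new cycle, dosing should be delayed for 1 week".

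**The concern.** Day 35 is 7 days past the end of a 28-day cycle and 14 days past the last scheduled lenalidomide day. A site with a patient who recovers from one of the six events has to decide three things the protocol does not settle: whether lenalidomide is taken on Days 22-28, whether Days 29-35 belong to the old cycle or the new one, and when the next Day 1 falls. In cycles 1 and 2 the site has no discretion to set the table aside.

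At stake are consistent dosing after a toxicity and the patient's rest week. If cycles are lengthened for some patients, the calendar time of the 2-cycle and 4-cycle response checks also moves for them.

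**Working it through.** The plan states no figure to reproduce here, so the check compares rules and counts days.

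**Does another rule supply a 35-day cycle?** No section defines one. Section 8.11 can move Day 1 by a week (28 + 7 = 35), but only when the new-cycle criteria are not met, whereas the six rows apply once the event has resolved. In at least four rows (platelets, rash, neuropathy, allergic reaction) the restart threshold is the same as the Section 8.11 threshold for that event, so a recovered patient gets no delay on that account. In the other non-hematologic row the thresholds differ. Restart is allowed at Grade 2 or lower, while Section 8.11 needs Grade 1 or lower, or baseline, if the event is drug-related. On Days 29-34 one rule could restart the old cycle while the other holds back the new one.

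**How much of the restart period lies outside the dosing days?** Resolution before Day 35 means by Day 34.
- After the last scheduled dose: Days 22-34, which is 34 - 22 + 1 = 13 days.
- On or after the next scheduled Day 1: Days 29-34, which is 34 - 29 + 1 = 6 days.

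**Worked example.** Inputs: event on Day 8 and restart on Day 15 (both assumed); 25 mg reduced to 15 mg (Section 8.1); reduced level carried into the next cycle (Section 8.11). All paths are counted over the same Days 1-35.

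| Path | Dosing days | Doses | Total |
|---|---|---|---|
| Unmodified schedule | 1-21, 29-35 | 21 + 7 = 28 | 28 × 25 = 700 mg |
| Row, dosed daily through Day 35 | 1-7, 15-35 | 7 + 21 = 28 | 7 × 25 + 21 × 15 = 490 mg |
| No make-up, next cycle on time | 1-7, 15-21, 29-35 | 7 + 7 + 7 = 21 | 7 × 25 + 14 × 15 = 385 mg |

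The second path exceeds the third by 28 - 21 = 7 doses and 490 - 385 = 105 mg. All seven fall on Days 22-28, the rest week.

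**Can the reduced-dose total exceed schedule?** With first omitted dose on Day *e*, restart on Day *r*, starting dose *H* and reduced dose *L*, the 35-day total is (*e* - 1)*H* + (36 - *r*)*L*. It is largest for the latest event and shortest gap, *e* = 14 and *r* = 15, giving 13*H* + 21*L*. The schedule is 28*H*.
- 25 to 15 mg: 325 + 315 = 640 against 700 mg (-60).
- 15 to 10 mg: 195 + 210 = 405 against 420 mg (-15).
- 10 to 5 mg: 130 + 105 = 235 against 280 mg (-45).

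At a reduced dose the total is always below schedule.

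**The case against.** The strongest reply is that a dose-modification table exists to depart from the default schedule. A specific instruction for a recovered patient can be read as an exception to the general 28-day rule, and Section 8.0 gives the table force. On that reading the cycle ends on Day 35 and the next Day 1 is naturally Day 36. Nor is the 28-day interval rigid, since Section 8.11 already lets Day 1 slip by a week, and by up to 4 weeks before removal. The ±4-day window in Section 4.1 governs visits rather than cycle length, so it settles little.

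Much of this stands. A reader might infer that a site simply cannot comply with both sets of rules, or that nothing could authorise a longer cycle. The documents do not support that, because the exception reading is available. What it does not do is make the rows usable. They give no lenalidomide days after Day 21 and no dexamethasone day after Day 22, they do not state the next Day 1, and they use Omit where the adjacent Hold/Delay definition would allow make-up doses.

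Three further inferences go too far:
- **Overdose.** If febrile neutropenia is managed with G-CSF and the dose is maintained, one omitted dose would give 34 × 25 = 850 mg against 700 mg. That is only a bound. The row calls for weekly blood counts, and 7 omitted doses give 28 × 25 = 700 mg, equal to schedule.
- **Uninterrupted dosing for 35 or 42 days.** Counting from Day 15 to Day 49 or Day 56 assumes daily lenalidomide through Day 35, which the rows do not spell out, and then an immediate new cycle. The 35-day count also makes Days 29-35 serve both cycles. The patient in the example has just had 7 drug-free days.
- **Displaced pembrolizumab.** Section 7.1 gives it every 21 days whatever the cycle, so a longer cycle changes visit labels, not infusion dates.

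There are real safeguards. Recovery is required before restart and follow-up is weekly. Section 15.28 limits each lenalidomide fill to a 28-day supply on a new prescription, so extended dosing would need prescriber action.

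**Conclusion.** The conflict is real and lies in the text of six rows. It is more than missing detail. In the two cycles where the table is binding, following the rows literally either puts lenalidomide into the rest week just after a toxicity or lengthens the cycle against the stated schedule.

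The size is modest. In the example it is 7 doses (105 mg) relative to no make-up, assuming daily dosing through Day 35, the Section 8.11 criteria met and no further interruption. Seven is also the most the rest week can hold. The documents give no frequency for these events on Days 2-14, so the number of affected patients cannot be estimated. The error rates in Section 16.22 depend on success counts and not on cycle length, so they are unaffected.

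**What to change.** In the six rows, replace Day 35 with a limit that fits the 28-day cycle. One form: restart at the next lower level only if the event has resolved before Day 21, and continue lenalidomide through Day 21; otherwise omit it for the rest of the cycle and apply Section 8.11. The column for Day 15 or later already works this way in five of the six rows; the allergic reaction row there does not cite Section 8.11.

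If a 35-day extension is intended, authorise it in Section 7.1, replace Omit in these rows, and state the lenalidomide and dexamethasone days and the next Day 1. The choice is clinical and belongs to the sponsor.

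The cost is a wording amendment to one column of one table, with no added patients, visits or procedures. The downside of the Day 21 limit is less lenalidomide for affected patients: 21 rather than 28 doses over 35 days in the example.
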